FILLGEL CIP #22E0978	Final version 2.0 Date: 21/09/2022	Confidential
LABORATOIRES SA	CIP #22E0978	Date: 21/09/2022	Page 12/74

## 1.5 OVERALL SYNOPSIS OF THE CLINICAL INVESTIGATION

ANSM registration #:	2022-A01183-40		
Clinical investigation plan #:	22E0978		
Title of the clinical investigation:	SAFETY AND EFFECTIVENESS CLINICAL EVALUATION OF THE RANGE OF INJECTABLE MEDICAL DEVICES FILLGEL IN FACIAL AESTHETIC TREATMENT		
Sponsor:	KYLANE LABORATOIRES SA [name] SWITZERLAND		
Development phase	Exploratory study		
Objectives:	The primary objective is to evaluate the effectiveness of the FILLGEL range used on different treated zones one month (M1) after treatment using clinical evaluation of the global aesthetic improvement (GAIS) rated by the independent investigator.		
	
 
The secondary objectives of the study are to collect data for the FILLGEL range on: 
 
the effectiveness of the range used on different treated zones six months (M6) and twelve months (M12) after treatment using clinical evaluation of the global aesthetic improvement (GAIS) rated by the independent investigator.
 
the safety using clinical evaluation of the Injection Site Reactions (ISR) rated by the subject and the investigator, and by collection of adverse events (AEs) at M1, M6 and M12.
 
subject's satisfaction and subject's opinion on aesthetic improvement on the different treated zones using clinical evaluation of the GAIS at M1, M6 and M12.
 
the injector's satisfaction on the injection quality using subjective evaluation questionnaire,
 
 
 
Another objective will be to illustrate the device effectiveness by realization of face macrophotographs.
 
		
Design:	
 
Open study,
 
intra-individual,
 
single dose,
 
single centre.
 
		
Planned Sample Size:	
 
68 subjects in total divided in 4 subgroups of 17 subjects, according to the kind of filler injected:
 
Group 1: 17 subjects treated in peri-oral lines by FILLGEL 0
 
Group 2: 17 subjects treated in nasolabial folds and/or in lips by FILLGEL 1 (with at least 10 in nasolabial folds and 7 in lips, both indications possible on the same subjects).
 
Group 3: 17 subjects treated in cheek/cheekbones by FILLGEL 2.
 
Group 4: 17 subjects treated in cheek/cheekbones and/or chin by FILLGEL 3 (with at least 10 in cheeks/cheekbones and 7 in chin, both indications possible on the same subjects).
 
		
Number of investigational study sites:	1 (Eurofins Dermscan Pharmascan)		

🛟 eurofins	Dermscan	PRM03-F-227_V6_EN
	Pharmascan	Clinical investigational plan for MD

KYLANE LABORATOIRES SA	FILLGEL CIP #22E0978	Final version 2.0 Date: 21/09/2022	Confidential Page 13/74	
Inclusion criteria:	
 
3. Age: bet
 
4. Subject s filler. 
 
*For gro
 
(score 3)
 
*For gro
 
(score 3)
 
1 or 2 for seeking s 
 
*For gro
 
cheeks/c
 
lipoatrop
 
*For gro
 
cheeks/c
 
lipoatrop
 
*For gro
 
cheeks/c
 
lipoatrop
 
enhance
 
 
 
5. Subject s 
 
who agre
 
6. Subject s
 
9. Women method througho
 
 
 
In terms of p 
 
1. Pregro
 
the s
 
2. Subject s
 
adm
 
gual
 
3. Subject s
 
Subject s
 
5. Subject s
 

	e or female. ween 18 and 65 years. seeking an improvement of up 1 : Subject with moderat to 5 on Bazin Upper lip sca up 2 : Subject with moderat to 4 on WSRS scale) and/o or superior and/or inferior an improvement of lip volun roup 3: Subject with theekbones volume deficit hy scale); roup 4: Subject with theekbones volume deficit hy scale) and/or subject so ment. whose weight did not fluctu ees to keep a stable weight having given their free, expr psychologically able to up o the study, and to give their registered with a social secu of childbearing potential so considered effective since ut the study. opulation gnant or nursing woman or p study. ject who had been depu inistrative or legal decordianship. ject in a social or sanitary e ject suspected to be non- stigator's judgment. ject having received a pensations for their partici ian beings in the last 1 cipation in the present stud	Page 13/74 her/his face aspect with HA te to severe peri-oral lines e); e to severe nasolabial folds subject with thin lips (score p on the Rossi scale) and e; moderate to severe (score 3 to 4 on Ascher eking improvement of chin ate in the last 6 months and during the study. ess, and informed consent. nderstand the information written informed consent. nderstand the information written informed consent. rity scheme. hould use a contraceptive e at least 4 weeks and during a pregnancy during ved of their freedom by sion or who is under stablishment. compliant according to the total of 4.500 euros as pation in research involving 2 months, including their A yor whose non-enrollment ir or any other lesion on the	
	stud (tatt In terms of a 8. Sub any the 9. Sub dise 10. Sub infed diso mor 11. Sub stre 12. Sub	ied zones which might in bo, permanent make-up). Issociated pathology ject suffering from a seven other pathology that may in study results and/or subject ject with known history of o ase and/or immune deficier ject suffering from active dis ction, tumours, inflammatory rders (herpes, acne, rosat ths before screening visit. ject with a history of strepto bococcus infection.	e or progressive disease or terfere with the evaluation safety. r suffering from autoimmune ncy. sease such as inflammation, and/or infectious cutaneous cea, porphyria) in the 6 pococcal disease or an active	

🛟 eurofins 📗	Dermscan	PRM03-F-227_V6_EN
	Pharmascan	Clinical investigational plan for MD

KYLANE LABORATOIRES SA	FILLGEL CIP #22E0978	Final version 2.0 Date: 21/09/2022	Confidential Page 14/74

 
anaesthetics (EMLA®), related to previous treatments.
 
15. Subject with previous hypersensitivity reacting to previous or ongoing treatment
 
16. Any medication which may interfere, at the interpretion the investigator, with the study objectives.
 
17. Subject having received treatment with a laser, or radiofrequency treatment, a dermabrasion, a chemical peeling or any other procedure based dermal response on the face within the past 18 planning to receive during the study any injection of those in the study protocol including non-perma (e.g., HA, Calcium Hydroxyapatite), autolo mesotherapy or botulinum neurotoxin on or near zone.
 
19. Subject having received at any time or planning to previoue data any time or planning to mesotherapy and polymethylmethacrylate, silicone) during the study 20. Subject with subcutaneous retaining structure or (meshing, threads, gold strand).
 
21. Subject using medication such as aspirin, nonste
 
		ere allergy or anaphylactic resensitivity to one of the ional device (i.e. HA), to tyl ® ) or to amide-type d to previous or current persensitivity reactions to a COVID-19 vaccination. ent rfere, at the interpretation of objectives. nent with a laser, ultrasound dermabrasion, a surgery, a procedure based on active hin the past 6 months or who procedures during the study. in the past 18 months of study any injections outside cluding non-permanent fillers yapatite), autologous fat otoxin on or near the treated time or planning to receive a ce (e.g., polylactic acid ne) during the study. aining structure on the face as aspirin, nonsteroidal anti- Ds), antiplatelet agents s within one week prior to cuser. eatment on the test area or a cation and/or antihistamines and during the study,	
Investigational device: Name / code Galenic form	mon 24. Subj stud 25. Subj than 10 c FILLGEL ra 1. FILLGEL	nsive exposure to sunlight o th and/or planning to do so ject planning to change h y. ject with an excessive cor	r UV-rays within the previous during the study. er/his life habits during the nsumption of alcohol (more ) and/or tobacco (more than s in syringe s
Indication		2: Indication: Cheeks, chee	

🛟 eurofins	Dermscan	PRM03-F-227_V6_EN
	Pharmascan	Clinical investigational plan for MD

KYLANE LABORATOIRES SA	FILLGEL CIP #22E0978	Final version 2.0 Date: 21/09/2022	Confidential Page 15/74	
	4. FILLGEL 3: Indication: Cheeks, cheekbones / chin			
Endpoints:	Proportion with the ov independen An improve	Primary endpoint: Proportion of subjects having an improvement of the zone treate with the overall FILLGEL range of devices as assessed by the independent investigator, one month after treatment, using the GAI An improvement is defined as a subject with "very much improved "much improved" or "improved" score on the GAIS.		
		ty of the FILGEL range ar	nd of each FILLGEL device	
	(IS mo • col inv mo	
 
independently will be assessed by:
 
collection of immediate and early Injection Site Reactions (ISRs) by the subjects on a daily-log every day up to one month after treatment.
 
collection of immediate and early ISRs by the independent investigator immediately and one (M1), six (M6) and twelve months (M12) after treatment.
 
collection of AEs throughout the study.
 
Proportion of subjects having an improvement of the zone treated with the overall FILLGEL range of devices as assessed by the independent investigator, six and twelve months after treatment, using the GAIS.
 
		
	with the ov independer			
	with each F assessed B	- Proportion of subjects having an improvement with each FILLGEL device for the four indication assessed by the independent investigator, or months after treatment, using the GAIS.		
	with the F	- Proportion of subjects having an improvement of the zone trea with the FILLGEL range of devices overall as assessed by subjects, one, six and twelve months after treatment, using the GA		
	with each F assessed	
 
Proportion of subjects having an improvement of the zone treat with each FILLGEL device for the four indications independently assessed by the subjects, one, six, and twelve months at treatment, using the GAIS.
 
Evaluation of the effectiveness on wrinkles/lines filling of the dev FILLGEL 0 used in the peri-oral lines as assessed by the independent investigator one, six and twelve months after treatment using the Bazin Upper lip wrinkles scale.
 
		
	FILLGEL ( independer			
	1 used in	the nasolabial folds as as one, six and twelve month	s filling of the device FILLGEL sessed by the independent ns after treatment, using the	
	FILLGEL 1		olume increase of the device the independent investigator ent, using the Rossi scale.	
	FILLGEL 2 independer	- Evaluation of the effectiveness on volume restauration of the FILLGEL 2 used in the cheeks/cheekbones as assessed independent investigator, one, six and twelve months after treat using the Ascher lipoatrophy scale.		

🚯 eurofins	Dermscan	PRM03-F-227_V6_EN
	Pharmascan	Clinical investigational plan for MD

KYLANE LABORATOIRES SA	FILLGEL CIP #22E0978	Final version 2.0 Date: 21/09/2022	Confidential Page 16/74
	FILLGEL 3 independent	- Evaluation of the effectiveness on volume restauration of the device FILLGEL 3 used in the cheeks/cheekbones as assessed by the independent investigator, one, six and twelve months after treatment, using the Ascher lipoatrophy scale.	
		atisfaction on the injection mmediately after injection o	quality using a questionnaire n D0.
		of the treatment effect one ompared to baseline by pho	, six and twelve months after tographs taking.
Study Procedures:	Screening, [	00, D7 (phone call for safet	y), M1, M6, M12
Statistical methods:	The statistic	al analysis will be performe	d by the CRO biostatistician.
	on the ITT a The analysi performed o	The analysis of the primary performance parameter will be performed on the ITT and PP population. The analysis of the secondary effectiveness parameters will be performed on the ITT and PP population. In case the ITT and PP population differ by less than 10%, only the PP population will be	
	The analysis the "safety"		ameters will be performed on
	subject's ch	A descriptive analysis of the population will be performed, includin subject's characteristics, subject's disposition, deviations to the protocol, injections characteristics.	
	For the prin	For the primary evaluation criteria:	
	For the para after injectio	For the parameter GAIS investigator with the 5 level scores (at D after injection, M1, M6 and M12), the frequencies and percentage will be presented for the overall face score and for the scores b	
	GAIS subje (1=Improver Improved) au parameters	Two derived parameters will be defined based on the parameters GAIS subject and investigator as a scores of 2 levels (1=Improvement (Very much improved, Much improved and Improved) and 2=No change or worsening). At each time point, these parameters will be described in frequencies, percentages and Confidence Interval (CI) 95%.	
	Inferential a	analysis for the primary ev	valuation criteria
	the GAIS In 50% will be	For the new derived parameters at M1 (1 month after injection) for the GAIS Investigator, a binomial exact test (bilateral approach) vs 50% will be applied at each time point for the overall face score . This test will compare the proportion of improvement to 50%.	
	For the sec	ondary evaluation criteria	:
	All the varial to their type Statistical te	All the variables will be described using adapted statistics according to their type (quantitative data or qualitative data). Statistical tests will be performed, to assess the change from baseline (Wilcoxon signed rank test).	
	The bilateral	l approach will be used with	a significance level of 0.05.

🔅 eurofins   Dermscan	PRM03-F-227_V6_EN
Pharmascan	Clinical investigational plan for MD

KYLANE	FILLGEL		Final version 2.0	Confidential
LABORATOIRES SA	CIP #22E0978		Date: 21/09/2022	Page 17/74
Estimated dates of the	Estimated dates of the study:		tigation beginning: Q4 202 tigation end: Q4 2023/Q1 2 truitment period duration: 3 tigation overall duration: 12 subject: 12 months + screer	2024 months months + recruitment period

🛟 eurofins	Dermscan	PRM03-F-227_V6_EN
	Pharmascan	Clinical investigational plan for MD

KYLANE	FILLGEL	Final version 2.0	Confidential	
	CIP #22E0978	Date: 21/09/2022	Page 18/74	
LABORATOIRES SA	CIF #22E0978	Date. 21/09/2022	Fage 10/74	

FLOW-CHART							
Procedure	Visit 1 Screening	Visit 2 Day 0	Phone call Day 7	Visit 3 M1	Visit 4 M6	Visit 5 M12	
Days	D-x	D0	D7 ± 1	D30±7	D180±14	D365±14	
Informed consent form signature	•						
Medical examination	•						
Medical history and previous and concomitant treatments collection	•						
Verification of the inclusion and exclusion criteria	•						
Urinary pregnancy test (for women with childbearing potential)		●p					
Confirmation of eligibility		●b					
Photographs (full face + 2 profiles)		●b		•	•	•	
Scoring of effectiveness using specific scales		●b		•	•	•	
Injection		٠					
Injector satisfaction questionnaire		●a					
GAIS live assessment by the independent investigator		●a		•	•	•	
GAIS assessment by the subjects				•	•	•	
Distribution of a subject daily-log	•	•		•	•	•	
ISR collection by subject		Each day di	● uring one month afte the daily-log	r injection, on			
ISR investigator		● a		•	•	•	
AE and concomitant treatments and procedures collection	•	•	•	•	•	•	

a : after injection, b : before injection AE: Adverse Event - GAIS: Global Aesthetic Improvement Scale- ISR: Injection Site Reaction

🛟 eurofins	Dermscan
	Pharmascan

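### The primary objective and endpoint concern the treated zone at M1, but the primary test is on an overall face score that the supplied synopsis neither defines nor equates with it

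*Combined protocol and SAP*

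**What the plan says.** All references are to section 1.5, the overall synopsis.

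- **Objectives.** The primary objective is to "evaluate the effectiveness of the FILLGEL range used on different treated zones one month (M1) after treatment", using the GAIS rated by the independent investigator.
- **Endpoints, primary.** "Primary endpoint: Proportion of subjects having an improvement of the zone treate with the overall FILLGEL range of devices", by the same rater on the same scale one month after treatment. The three favourable GAIS categories count as improvement.
- **Endpoints, secondary.** The other range-level GAIS endpoints are also worded for the zone. One is "improvement of the zone treated with the overall FILLGEL range of devices as assessed by the independent investigator, six and twelve months"; the subject-rated one concerns the treated zone "with the FILLGEL range of devices overall as assessed by subjects".
- **Statistical methods, primary criteria.** Frequencies of the five-level investigator GAIS "will be presented for the overall face score and for the scores b". The text breaks off there in extraction, so the label of the second set of scores is lost.
- **Statistical methods, inferential analysis.** A two-sided exact binomial test of the two-level investigator GAIS against 50% is introduced for M1 and then said to be one that "will be applied at each time point for the overall face score".
- **Planned sample size.** There are four groups of 17. Groups 2 and 4 each cover two indications, with "both indications possible on the same subjects".
- **Flow-chart.** There is one line, "GAIS live assessment by the independent investigator", with no division into zone and face.

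**The concern.** The objective and endpoint ask whether the treated zone improved. The test asks whether something called the overall face score improved. In the endpoint, overall qualifies the range of devices; in the test, it qualifies the face. Each group is injected only in limited areas, so an investigator could reasonably rate zone and face differently.

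If the face score is a separate rating, a significant result would not by itself support the treated-zone claim, and a non-significant one would not refute it. If the label stays undefined until data are in, the variable behind the primary test could be settled after the results are known. The inferential sentence has a second loose end: it gives both M1 and every time point for what is meant to be a single primary test.

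**Working it through.** **1. Endpoint and test side by side**

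| Element | Objective and endpoint | Primary test |
|---|---|---|
| Rater | Independent investigator | Investigator |
| Scale | GAIS | GAIS |
| Cut | Three favourable categories | Same two-level split |
| Time | M1 | M1, but also each time point |
| What is rated | Treated zone | Overall face |
| Pooling | Whole device range | Not stated separately |

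Rater, scale and cut agree. Time agrees only in part: the investigator GAIS is collected at D0 after injection, M1, M6 and M12. What is rated does not agree in words, and nothing in the supplied pages bridges the gap.

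**2. Sample size**

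4 × 17 = 68, as stated. The supplied pages give no expected rate, power or dropout, so nothing further can be reproduced. The figures below assume that all 68 are evaluable.

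**3. Where the test turns**

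Inputs from Statistical methods: reference 50%, two-sided, level 0.05. Against 0.5 the two-sided exact p-value for a count k above 34 is 2 × P(X ≥ k), with X ~ Bin(68, 0.5).

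- k = 43: 2 × 0.0192 = 0.0385; observed 43/68 = 63.2%, exact 95% CI 50.7% to 74.6%.
- k = 42: p = 0.068; exact 95% CI 49.2% to 73.3%.

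The favourable boundary is therefore 43/68. If k subjects improve in the zone, the face count must be lower by a net k − 42 subjects to lose significance: 1 at 43, 6 at 48 (70.6%), 12 at 54 (79.4%) and 19 at 61 (89.7%).

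**4. How close to the boundary the trial might be**

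The true rate is assumed, because the documents give none. The result is P(X ≥ 43) with X ~ Bin(68, p).

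| True rate p | Chance of reaching 43/68 |
|---|---|
| 50% | 0.02 |
| 60% | 0.34 |
| 65% | 0.67 |
| 70% | 0.91 |
| 75% | 0.99 |
| 80% | 0.9996 |

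If both ratings have a true rate of 80%, each misses the boundary with probability 1 − 0.9996 = 0.0004. The chance that they give different verdicts is then at most 2 × 0.0004 = 0.0008, however poorly they agree within subjects.

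**5. Subjects with two treated zones**

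In Groups 2 and 4 the minimum numbers are 10 + 7 = 17, so there may be no two-zone subjects at all. At most there are 17 + 17 = 34 of 68. If the GAIS is recorded per zone, the rule for combining zones affects the proportion. The extreme case is an assumed 70% per zone, all 34 subjects with two zones, and independent zones:

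- Improved in every zone: (34 × 0.70 + 34 × 0.49)/68 = 59.5%.
- Improved in any zone: (34 × 0.70 + 34 × 0.91)/68 = 80.5%.

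With no two-zone subjects, or with zones that always agree, both rules give 70%.

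**The case against.** The best defence is that there is only one variable. The test stands under the primary-criteria heading, and rater, scale and cut match. The plan speaks of a single investigator GAIS parameter, the flow-chart has one line for it, and no supplied page lists a second, whole-face rating. The Endpoints row pairs range-level results with per-device results, so overall may simply mean pooled over the range. The words that would show what the overall score is contrasted with are lost in extraction, which is no fault of the plan. Only a synopsis is supplied, and the body may define the score. The study is also labelled exploratory.

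Much of this stands. A reader might infer that the plan definitely tests a variable other than its declared endpoint. The documents do not support that: absence of a stated equivalence is not a stated difference, and the lost label could point either way. Nor do they show that zone and face ratings diverge, so no particular loss of power or change of verdict can be attributed to the wording.

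What the defence does not explain is the word face. Pooling over devices does not turn a zone rating into a face rating, and the descriptive analysis still sets the face score beside at least one other set of GAIS scores. An exploratory study that declares a primary endpoint, a 50% reference and a 0.05 level still needs to say which variable is tested.

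**Conclusion.** The point holds in a limited form. In the supplied synopsis, the variable named in the primary test is not shown to be the one named in the primary objective and endpoint. It is tempting to go further and say that the primary test is invalid or answers the wrong question. That would follow only if the face score is a separate rating, which the supplied pages neither state nor exclude.

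The practical effect is conditional. With 68 evaluable subjects, the choice changes the verdict only if the two ratings differ and the rate is near 63%. At about 80% or more for both, it rarely does. All true rates used here are assumptions. The matter should still be settled before data are seen, because it concerns the only primary test and the correction is small. Confidence is moderate, since most of the plan was not available. The conflict between M1 and every time point is plain in the text and needs correcting in either case.

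**What to change.** Unless the full plan already equates the two, do the following before data are seen.

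1. Name one variable throughout. Suggested wording: *The two-sided exact binomial test against 50% will be applied at M1 to the independent investigator's GAIS for the treated zone(s), one result per subject, pooled over the four groups. Any separate whole-face score will be reported as supportive.* If the overall face score is only another name for this rating, say so in the same place. If a whole-face rating is what is intended, reword the primary objective and endpoint to match.
2. Delete the reference to each time point from the primary test, or label tests at the other time points as secondary.
3. If the GAIS is recorded per zone, fix one rule in advance for Group 2 and Group 4 subjects with two treated zones. Improvement in every treated zone is one option; another is acceptable if it is stated beforehand.

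The cost is one or two sentences. If the test is on the zone and the form does not already capture a zone GAIS, a form field is also needed. A strict rule for two-zone subjects may lower the headline proportion, by an amount that depends on how many there are and how closely their zones agree.

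### Does the immediate-and-early wording at M6 and M12, together with the later daily-logs, leave late injection-site reactions out of the safety results?

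*Combined protocol and SAP*

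**What the plan says.** All the relevant text is in Section 1.5 and the flow-chart that follows it.

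- **Objectives (secondary).** Safety is to be studied through ISRs "rated by the subject and the investigator, and by collection of adverse events (AEs) at M1, M6 and M12". Nothing here restricts when a reaction must start.
- **Endpoints, investigator.** The endpoint is "collection of immediate and early ISRs by the independent investigator immediately and one (M1), six (M6) and twelve months (M12) after treatment".
- **Endpoints, subject.** The matching item, listed just before it, is "collection of immediate and early Injection Site Reactions (ISRs) by the subjects on a daily-log every day up to one month after treatment".
- **Endpoints, AEs.** The third safety item is "collection of AEs throughout the study". Safety is to be assessed for the range and for each device.
- **Flow-chart.** The row "ISR investigator" is marked at D0 after injection, M1, M6 and M12, with no qualifier. The row "Distribution of a subject daily-log" is marked at screening, D0, M1, M6 and M12. Subject ISR recording runs daily for one month after injection. AEs and concomitant treatments are collected at every visit and at the D7 call.
- **Design and sample size.** Each subject is treated once, at one centre, in an open study: 68 subjects in four groups of 17.

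**The concern.** With one injection, no new early period opens at M6 or M12. An endpoint that names only immediate and early reactions at those visits seems to exclude just what a late visit could add: a reaction that first appears months after treatment. Reading the phrase as early reactions followed through to M12 does not help, because it too has no place for a late onset. Such an event could then be recorded only as an AE. If it were sometimes entered as an ISR and sometimes as an AE alone, ISR rates per device could be too low and hard to compare by time of onset. With 17 subjects per device, one event is visible in the rate.

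The daily-logs add to the impression of a muddled schedule. Subject recording stops at one month, yet logs are handed out at M1, M6 and M12, and the synopsis and flow-chart give no purpose for them. A reader could suspect either a lost data stream on late reactions or a conflict over how long subjects are meant to record.

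**Working it through.** The documents state no figure to reproduce. The check compares passages and does some arithmetic on visit windows and group sizes.

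**1. Is a late reaction lost?**

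| Source | Investigator ISRs at M6 and M12 | Limit on onset |
|---|---|---|
| Objectives | ISRs rated by investigator | none |
| Endpoints | yes | immediate and early |
| Flow-chart | marked at both visits | none |
| AE endpoint and flow-chart row | AEs throughout and at both visits | none |

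All three ISR sources are compatible with the investigator assessing ISRs at M6 and M12; the endpoint and flow-chart say so outright. The AE row covers the same visits without restriction. A reaction seen at M6 or M12 is therefore recorded under any reading. The open question is whether it is labelled an ISR or only an AE.

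**2. How far could labelling move a rate?** Assume k subjects whose only ISR starts late and is entered as an AE alone. The shift is k/n.

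- Device, n = 17: k = 0 gives 0; k = 1 gives 1/17 = 5.9 points; k = 2 gives 2/17 = 11.8 points.
- Range, n = 68: k = 0 gives 0; k = 1 gives 1/68 = 1.5 points; k = 2 gives 2/68 = 2.9 points.

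The documents give no value for k. A subject counts towards k only if he or she had no ISR at all in the first month; otherwise the subject is already in the numerator and the rate does not change.

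**3. Is dating made worse by the wording?** The windows are M1 = D30±7 (D23 to D37), M6 = D180±14 (D166 to D194) and M12 = D365±14 (D351 to D379).

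- M1 to M6: nominal 180 − 30 = 150 days; range 166 − 37 = 129 to 194 − 23 = 171.
- M6 to M12: nominal 365 − 180 = 185 days; range 351 − 194 = 157 to 379 − 166 = 213.

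These intervals come from the visit schedule. Removing the qualifier would leave them unchanged, so they do not measure its effect.

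**4. What are the later logs for?** Taking one month as 30 days, a log given at M1 has at most 30 − 23 = 7 days of ISR recording left. One given at M6 comes at least 166 − 37 = 129 days after the M1 window closes, and one given at M12 at least 351 − 37 = 314 days after. For ISR recording alone, the M6 and M12 logs have no use. Compare the marks, however:

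| Row | Screening | D0 | D7 call | M1 | M6 | M12 |
|---|---|---|---|---|---|---|
| Log distribution | yes | yes | no | yes | yes | yes |
| AEs and concomitant treatments | yes | yes | yes | yes | yes | yes |

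The rows agree everywhere except the D7 telephone call, when no paper can be handed over. A log is also given at screening, before any ISR can exist. This fits a log that also serves for AE and treatment notes. On that reading the M1 and M6 logs cover the intervals to the next visit, and only the log at M12, the last scheduled visit, has no evident use.

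**The case for a change.** The strongest case for acting is that the mismatch can be checked word for word and is cheap to repair. The qualifier stands in the endpoint and nowhere else. Neither immediate nor early is defined in the synopsis or flow-chart; the nearest anchor is the one-month subject log, "by the subjects on a daily-log every day up to one month after treatment", and taking that as the end of early is an assumption. Safety is to be reported per device, where one subject is worth 5.9 points. One could also ask for ISRs tabulated by onset before and after M1, cross-referenced to AEs, and for the later logs to be used for dated entries whenever a reaction occurs.

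The textual point stands, and so does the unexplained M12 log. The step from there to a harmed result does not. The investigator item shares its opening phrase with the subject item listed just before it, so carried-over wording is at least as plausible as a decision to exclude late reactions. This is a single-centre study and the endpoint refers to one independent investigator, so different raters sorting like events differently is less likely than in a multicentre trial. The onset table and the event-driven log would be additions; neither corrects a wrong result.

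**Conclusion.** No change to the plan follows. There is a wording mismatch between the safety endpoint on one side and the objective and flow-chart on the other, plus one stray-looking log distribution at M12. The sponsor may tidy both when the document is next edited. Followed as written, the plan still has ISRs assessed at M6 and M12 and AEs collected throughout, so late reactions reach the safety data. An analyst who reads the endpoint beside the objective and flow-chart would sensibly count ISRs of any onset at those visits.

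The possible effect is limited to labelling: 0, 5.9 or 11.8 points for a device and 0, 1.5 or 2.9 points for the range, for 0, 1 or 2 assumed subjects. Nothing in the documents shows that the count exceeds zero. The primary endpoint, its test and the sample size are untouched.

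This conclusion rests on two assumptions. The first is that AE collection takes in reactions at the injection site, which an unrestricted AE endpoint implies. The second is that the log has a use beyond ISRs, which the pattern of marks suggests but does not prove. Only synopsis and flow-chart pages (12 to 18 of 74) were available; the body of the plan may define the terms and state the purpose of the log.

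### The synopsis runs the primary M1 GAIS test on both ITT and PP without saying which result decides, and leaves the handling of a missing M1 rating open

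*Combined protocol and SAP*

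**What the plan says.** All of the relevant text is in section 1.5 (overall synopsis), under Endpoints and Statistical methods.

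- **Endpoint.** The primary endpoint is the proportion of subjects improved on the independent investigator's GAIS one month after treatment, for the whole device range.
- **Analysis sets.** "The analysis of the primary performance parameter will be performed on the ITT and PP population". The sentence gives no order of priority and does not say that both must succeed. ITT and PP are not defined in the supplied text.
- **10% rule.** After the sentence on the secondary effectiveness parameters comes "In case the ITT and PP population differ by less than 10%, only the PP population will be", where the extracted text breaks off. This is the only statement that ranks the two sets, and it prefers PP.
- **Derived variable.** The GAIS is reduced to "scores of 2 levels (1=Improvement (Very much improved, Much improved and Improved) and 2=No change or worsening". No value, imputation or denominator is given for a subject without an M1 rating.
- **Test.** For the overall face score, "a binomial exact test (bilateral approach) vs 50% will be applied at each time point for the" is specified, with "a significance level of 0.05". No analysis set is attached to it.
- **Context.** 68 subjects are planned in an open, single-centre study labelled exploratory. The supplied text gives no expected improvement rate, power or dropout rate.

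**The concern.** One primary question can receive two answers, and the synopsis does not say which prevails when they differ.

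In a randomised comparison, exclusions may fall on both arms and partly balance. Here a single proportion is compared with a fixed 50%, so nothing offsets them. If subjects who deviate or fail to return tend to be the non-improved ones, the PP proportion is biased upwards and PP is the anti-conservative set.

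The open handling of a missing M1 rating adds a second choice inside ITT. An unrated subject could be left out, counted as not improved, or given the investigator's post-injection D0 rating carried forward. The text excludes none of these, and they can give different primary results.

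**Working it through.** **Inputs from the synopsis:** N = 68; null value 50%; exact binomial, two-sided, alpha 0.05. The planned N cannot be reproduced, because no power, expected rate or dropout rate is supplied. **Assumptions:** all numbers improved, excluded or unrated, and all true rates, are mine.

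**Step 1: threshold on all 68.** Under a null of 0.5 the two-sided p-value is 2 × P(X ≥ x), with X ~ Bin(n, 0.5).
- 42/68 = 61.8%, p = 0.068.
- 43/68 = 63.2%, p = 0.0385.

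Success needs 43. The actual one-sided error is 0.0385 / 2 = 1.9%.

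**Step 2: exclusions related to outcome.** Suppose all 68 are rated and four non-improved subjects leave PP.
- 42/68, p = 0.068, becomes 42/64 = 65.6%, p = 0.017.
- 41/68, p = 0.114, becomes 41/64 = 64.1%, p = 0.033.
- 40/64 gives p = 0.060, so 40 improved fails on both sets.

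A win on either set then needs only 41 of 68. Under a true rate of 50% its one-sided error is 0.1143 / 2 = 5.7%, against 1.9% for ITT alone. This is an extreme case: with 42 of 68 improved, random exclusion of four would remove four non-improved subjects with probability C(26,4) / C(68,4) = 1.8%.

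**Step 3: exclusions unrelated to outcome.** All 68 are rated and PP drops d subjects at random. The one-sided error of winning on either set is:

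| d | ITT alone | Either set |
|---|---|---|
| 3 | 1.9% | 2.5% |
| 6 | 1.9% | 2.2% |
| 7 | 1.9% | 2.5% |
| 10 | 1.9% | 3.0% |
| 14 | 1.9% | 2.8% |

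Over these values of d, a PP win with an ITT miss has probability of about 1.5–5% at true rates of 60–65%, and 0.01% or less at 80% and above.

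**Step 4: missing M1 ratings.** Let m subjects be unrated, and compare the rated subjects with all 68, counting unrated as not improved.
- m = 3: 41/65, p = 0.046; 41/68, p = 0.114.
- m = 6: 40/62, p = 0.030; 40/68, p = 0.18.
- m = 10: 37/58, p = 0.048; 37/68, p = 0.54.

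Probability of winning on the rated subjects but missing on all 68, if unrated status is unrelated to outcome:

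| True rate | m = 3 | m = 6 | m = 10 |
|---|---|---|---|
| 60% | 17% | 19% | 31% |
| 65% | 20% | 31% | 54% |
| 70% | 12% | 25% | 58% |
| 80% | 0.2% | 1.4% | 10% |
| 90% | about 0 | about 0 | 0.01% |

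This table compares two denominators. It shows what the missing-rating rule is worth and is not by itself an ITT/PP conflict.

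**Step 5: power of each handling with six unrated.**

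| True rate | Complete data, 68 | Observed cases, 62 | Missing as not improved, 68 |
|---|---|---|---|
| 65% | 0.67 | 0.59 | 0.28 |
| 70% | 0.91 | 0.86 | 0.61 |
| 80% | above 0.999 | 0.999 | 0.98 |

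**The case against.** **Only the synopsis is supplied.** It covers pages 12 to 18 of 74. A fuller statistical section may define the sets, rank them and give a missing-data rule. This stands, and the point is limited to the synopsis as supplied.

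**The 10% rule may already settle the matter.** It most naturally governs the secondary parameters, in which case both primary analyses are reported and an ITT miss would be visible. If it also covered the primary and counts subjects, up to six exclusions (6/68 = 8.8%) would leave PP alone: no conflict, but the more selected set would decide. The cut-off sentence does not allow certainty. Either reading calls for a clarifying line.

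**A reader might infer that unrated subjects drop out of ITT.** The documents do not say so. A two-level variable does not fix the denominator or rule out imputation; the handling is unspecified.

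**A reader might also infer that a PP win with an ITT miss would be claimed as success.** The supplied text states no success rule, so it neither permits nor forbids that claim.

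**The practical effect may be small.** The study is labelled exploratory, random exclusions add little error, and a high true rate makes the sets agree. All of this stands and lowers the weight of the point. It does not remove it: the plan still sets a primary endpoint, a null value and a 0.05 test, and the supplied text gives no expected rate to show that the threshold is far away.

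**Conclusion.** The point holds as a gap in the synopsis as supplied: the primary test has two analysis sets, no deciding one, and no stated handling of a missing M1 rating.

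Its size depends on assumptions that the documents do not settle. Near the 63% threshold, a few outcome-related exclusions reverse the result (42/68, p = 0.068, against 42/64, p = 0.017). With 3 to 7 exclusions unrelated to outcome, taking either set raises the one-sided error only from about 1.9% to 2.2–2.5%, and to at most about 3% with 10 or 14. At a true rate of 80% or more the ITT/PP conflict is negligible. The missing-rating rule can still matter at 80% if as many as ten subjects are unrated (10%), but not at 90%.

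This is a low-cost improvement that should be made. It is not evidence that the primary test is invalid.

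**What to change.** **Main change.** State that the ITT result, with ITT defined as all injected subjects, decides the primary objective; that PP is supportive; and that the 10% rule does not apply to the primary parameter.

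**Secondary change.** Fix the handling of a missing M1 GAIS before the data are seen. For example, report both the missing-as-not-improved and the observed-case proportions, and name which one leads so that the ambiguity does not reappear inside ITT.

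**Cost.** These are wording changes only, with no extra subjects or visits. The primary result may be slightly less favourable than PP would give. If missing-as-not-improved is made decisive, each unrated subject counts against the device: with six unrated and a true rate of 70%, power is 0.61, against 0.86 for observed cases and 0.91 with complete data. The sponsor should make that choice knowing this loss.
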